**Figure 3–1 Study Design: Study Periods and Visit Schedule**

Abbreviations: [REDACTED] BSL = Baseline; EOS = end of study; EOT = end of treatment; RAN = randomization; SOT = start of treatment.

\* Baseline assessments for fluorescein angiography, indocyanine green angiography, and color fundus photography will be collected at Screening (Visit 1) instead of Visit 2.

For subjects who used prohibited concomitant medications within 14 days prior to the planned randomization date, a washout period will be required prior to the first dose of study drug. The duration of this washout must be a minimum of 14 days for any prohibited ocular, nasal, and systemic medications (defined as those delivered by injection, oral, or transdermal methods) prior to the planned randomization date.

Approximately 35 subjects will be enrolled in the study. Once the Screening visit laboratory test results are confirmed, subjects who still meet all inclusion criteria and none of the exclusion criteria will be randomly assigned in a 3:3:1 ratio to receive one of the following treatment regimens:

1. MT-0814 [REDACTED] for 12 weeks (N=15)
2. MT-0814 [REDACTED] for 12 weeks (N=15)
3. Placebo [REDACTED] for 12 weeks (N=5)

[REDACTED]  
[REDACTED]  
[REDACTED]  
[REDACTED] Following training and under supervision, subjects will receive the first dose of study drug at the study site on Day 1 (Week 0). If a subject withdraws prematurely from the study before the completion of the treatment period (that is, before the Week 12 visit), a final visit must be scheduled for End of Study (EOS) assessments.

Efficacy, safety, and plasma concentration assessments will be performed as presented in the schedule of events (SOE) (Table 13–1); the plasma concentration sample collection schedule is presented in Table 13–2. Efficacy, safety, and plasma concentration measures are listed below.

- The primary efficacy measure is the assessment of change (from Baseline) in BCVA (measured by the Early Treatment of Diabetic Retinopathy Study [ETDRS]) at Week 12.
- The key secondary efficacy measure is the assessment of change (from Baseline) in the CSFT at Week 12.
- Additional efficacy/safety measures include assessment of the changes observed from Baseline at each visit for the following:

- Best-corrected visual acuity
- Central subfield thickness
- Optical coherence tomography (OCT) parameters

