## 7.4 Sample Size Calculations

The sample size for this study was not selected based on statistical power calculations, but rather on clinical considerations. Approximately 35 subjects will be randomly assigned (in a 3:3:1 ratio) to receive MT-0814 [REDACTED] MT-0814 [REDACTED] or placebo [REDACTED]. Randomization will be stratified by the BCVA score category (scores  $\leq 55$ , 56 to 70, or  $\geq 71$ ) observed for the subject's study eye on Day 1 (Baseline).

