## 7.6 Description of Subgroups to be Analyzed

Efficacy summaries will also be presented for the following subgroups:

- CNV type (predominantly classic, minimally classic, occult with no classic type; refer to Section 6.1.3)
- Presence/absence of PCV (only if a sufficient number of subjects with PCV are assessed)
- Presence/absence of RAP (only if a sufficient number of subjects with RAP are assessed)
- BCVA at Baseline (Day 1)
- Age
- Sex
- Body mass index

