## 7.9 Statistical Analysis Methodology

Statistical analysis will be performed using SAS software Version 9.4 or higher. Continuous variables will be summarized using the mean, standard deviation, median, minimum value, and maximum value. Categorical variables will be summarized using frequency counts and percentages. Data will be listed in data listings.

Details of the statistical analyses, methods, and data conventions are described in the statistical analysis plan (SAP).

All statistical tests will be 2-sided and performed using a 5% significance level, leading to 95% (2-sided) confidence intervals. Pairwise comparisons will be performed with no multiplicity adjustments. Additionally, no multiplicity adjustments will be performed for multiple endpoints.

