### 7.9.1 Analysis of Primary Efficacy Endpoint

The primary analysis will be performed on the study eye within the FAS. The following 2-sided hypothesis will be tested:

- H0: The difference in mean change from Baseline in BCVA in the study eye at Week 12 between placebo and MT-0814 is equal.
- Ha: The difference in mean change from Baseline in BCVA in the study eye at Week 12 between placebo and MT-0814 is not equal.

The primary analysis will be performed using an analysis of covariance (ANCOVA) model including fixed effect for treatment and Baseline BCVA score as a covariate. Subjects with missing data at Week 12 or who receive rescue therapy will have their data imputed by worst observation carried forward (WOCF) method. Only postbaseline observations observed prior to dropout or receipt of rescue therapy (whichever occurs first) will be carried forward. Additional sensitivity analyses such as the following may be performed:

- An ANCOVA on observed data
- A t-test on observed data
- The mixed models repeated measures (MMRM) including observed data for all visits through Week 12

- The ANCOVA at Week 12 incorporating data from the fellow eye with missing data at Week 12 imputed using WOCF. (This analysis will be dependent on the number of subjects who have both eyes meet all entry criteria.)
- Multiple imputations of missing data analyzed using the same ANCOVA model as for the primary analysis.

Analysis will be performed separately to compare each dose of MT-0814 to placebo (eg, including only subjects receiving placebo and subjects receiving the MT-0814 dose being compared to placebo.)

The change from Baseline in BCVA at Week 12 will be also be descriptively summarized by the subgroups presented in Section 7.6. Statistical hypothesis testing to compare each MT-0814 dose to placebo within subgroups will be performed by t-test if the subgroup size is sufficient.

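### Within-subgroup t-tests of each dose against 5 placebo subjects, unadjusted and with no minimum size, give misleading p-values and do not test whether the effect differs between levels

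*Combined protocol and SAP*

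**What the plan says.** Section 7.9.1 first calls for a descriptive summary of Week 12 BCVA change by subgroup, then adds: "Statistical hypothesis testing to compare each MT-0814 dose to placebo within subgroups will be performed by t-test if the subgroup size is sufficient". No number is attached to *sufficient*.

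Section 7.6 lists seven factors. One has three stated levels: "CNV type (predominantly classic, minimally classic, occult with no classic type; refer to Section 6.1.3". The others are PCV, RAP, Baseline BCVA, age, sex and body mass index. PCV and RAP carry their own size condition, also without a number, and Section 7.6 gives no cut-points for Baseline BCVA, age or body mass index.

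Section 7.4 says "Approximately 35 subjects will be randomly assigned (in a 3:3:1 ratio"), and Section 3.1 plans "Placebo [REDACTED] for 12 weeks (N=5") and, for each dose, "MT-0814 [REDACTED] for 12 weeks (N=15"). Section 7.9 adds "All statistical tests will be 2-sided and performed using a 5% significance level", "Pairwise comparisons will be performed with no multiplicity adjustments" and "no multiplicity adjustments will be performed for multiple endpoints". No treatment-by-subgroup interaction test is described.

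**The concern.** Five controls cannot be divided among subgroup levels and still support a useful comparison. Which tests are run depends on where the placebo subjects happen to fall. With no stated minimum, that choice can also be made after the data are seen.

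A significant result in one level and a non-significant result in another does not show that the effect differs between them, although it is easily read that way. Both doses are compared with the same few controls, so agreement between them would look like corroboration when part of it is shared error.

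In a proof-of-concept study, the risk is that a nominal p-value in one level is taken as a finding about who responds.

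**Working it through.** **Arm sizes.** 35 × 3/7 = 15, 35 × 3/7 = 15 and 35 × 1/7 = 5, which reproduces the planned 15/15/5.

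**Controls per level.** By counting, the smaller of two levels holds at most 2 of 5 placebo subjects, and the smallest of three at most 1. A minimum of 2 therefore always drops a level of every three-level factor, and a minimum of 3 always drops a level of every factor. For a 50/50 factor the count is Binomial(5, 0.5): 0 controls with probability 3%, 1 to 3 with 78%, 4 or 5 with 19%. In the simulation below, 79-88% of tests with at least one control rest on 1 to 3.

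**Precision and power of one test.** The 95% half-width in SD units is t(0.975; n1+n2−2) × √(1/n1 + 1/n2). Power is for a true difference of 1 SD, from the noncentral t.

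| Placebo v dose | Half-width (SD) | Power |
|---|---|---|
| 5 v 15 (whole study) | 1.08 | 45% |
| 3 v 8 | 1.53 | 26% |
| 2 v 7 | 2.365 × √(1/2 + 1/7) = 1.90 | 19% |
| 1 v 7 | 2.62 | 12% |

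The documents give no SD. At an assumed 8 to 15 letters, 2 v 7 gives about ±15 to ±28 letters.

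**Number of tests.** CNV type and Baseline BCVA at three levels each, plus age, sex and body mass index at two, make 12 levels. PCV and RAP make 16. With two doses that is 24 to 32 tests. If all ran and were independent, the chance of at least one p<0.05 would be 1 − 0.95^24 = 71% to 1 − 0.95^32 = 81%. These are not the working figures, because the tests are correlated and many levels lack controls.

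**Simulation with no true effect.** 3,000 trials of 5/15/15, normal outcomes, pooled t-tests and independent factors. Assumed frequencies: equal thirds for the three-level factors, 50/50 for age, sex and body mass index, PCV 20%, RAP 15%.

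| Minimum controls | Mean number of tests (12; 16 levels) | At least one p<0.05 (12; 16 levels) |
|---|---|---|
| 2 | 16.2; 20.7 | 43%; 46% |
| 3 | 8.3; 12.2 | 27%; 31% |
| 4 | 2.6; 5.9 | 10%; 16% |
| 5 | 0.4; 1.9 | 1.5%; 7% |

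Repeat runs put the first three rows at 42-46%, 25-32% and 10-16%. The error per test was 4.8-5.2% for minimums of 1 to 4. The excess therefore comes from the number of tests. If the placebo SD were 1.5 times larger, the per-test error would be about 9%, and the chance of any false positive about 56% (minimum 2, 12 levels).

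**Shared controls.** At 2 v 7, the correlation between the two dose differences is (1/2) / (1/2 + 1/7) = 0.78. In simulated levels with 2 controls, when one dose was significant the other was too in about 28% of cases, against 5% under independence.

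**One pooled model.** Assumed SDs: between subjects 12, change 8, reading 5. The SD of change is √(8² + 2 × 5²) = 10.68. In a level with 2 controls, the mean half-width falls from about 19.6 letters (t-test) to about 17.4 (one ANCOVA on all 35 subjects with interaction and Baseline BCVA), or 2.2/19.6 = 11%. Adjustment for Baseline BCVA lowers the residual SD only to √(114 − 25²/169) = 10.50, or 1.6%. Without the covariate the pooled half-width is essentially the same (17.2 v 17.3 in one run). The gain comes from the residual degrees of freedom: 35 − 7 = 28, against 7 at 2 v 7.

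**The case against.** The subgroup output is descriptive by default and testing is conditional on size, so the plan already recognises small cells. The study is a small proof of concept, not sized on power, and it openly forgoes multiplicity adjustment. Section 7.9 leaves detail to a SAP that, under Section 8, must be signed before database lock. All of this is fair. It does not supply a minimum size, and the text available here contains none. A strict minimum of 4 or 5 controls would largely remove the false positives, but would leave few tests to run.

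Several stronger readings are tempting, and the documents do not support them:
- **That every subgroup is tested.** The sentence is conditional, and PCV and RAP have a further condition.
- **That 1 to 3 controls is certain.** It is typical; a level can hold 0, 4 or 5.
- **That few controls inflate the error of each test.** Under normality and equal variance they do not; they cost power.
- **That one outlying placebo value makes a level significant for both doses.** If the other placebo value equals the dose mean and the outlier grows without limit, it inflates the pooled variance as well. |t| approaches only 2.33 against a critical 2.36 at 2 v 7, and 1.81 against 2.26 at 3 v 8.
- **That dropping Baseline BCVA is a material loss.** It is worth about 1.6% of the SD here, and the outcome is already a change from Baseline.
- **That a subgroup result would set the next trial's population.** No decision is attached to these tests.

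The pooled model has limits too. With three equal levels, 3 × (2/3)^5 − 3 × (1/3)^5 = 93/243 = 38% of trials leave some level without placebo, so a rule for that case is needed. A half-width of 17.4 letters is still wide beside about 1.08 × 10.68 = 11.5 for the whole comparison. Five to seven unadjusted interaction p-values would carry up to 1 − 0.95^5 = 23% to 1 − 0.95^7 = 30% if independent, so they must be labelled exploratory.

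**Conclusion.** The point stands as an analysis choice that should be changed. Followed as written, the sentence produces subgroup p-values that mostly rest on 1 to 3 shared controls, run where placebo subjects happen to fall, and do not compare effects between levels. The chance of at least one spurious p<0.05 depends chiefly on what *sufficient* turns out to mean: substantial at a minimum of 2 or 3 controls, modest at 4, small at 5.

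The counting argument needs only the planned 5 placebo subjects. The error rates rest on assumed level frequencies, independence between factors, normality and equal variance. The letter-scale widths rest on assumed SDs.

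**What to change.** In Section 7.9.1, delete the sentence on within-subgroup t-tests and specify instead:
- For each Section 7.6 factor, one ANCOVA on all randomised arms with treatment, subgroup, their interaction and Baseline BCVA.
- Level-specific differences of each dose from placebo with 95% CIs, labelled exploratory, and no within-level p-values.
- The interaction p-value only for factors in which every level contains placebo subjects. For other factors, levels without placebo are shown descriptively only.

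The cost is plan wording and a model change, with no new data. The downsides are that the model assumes a common residual variance across levels, and that it departs from the separate dose-versus-placebo data sets used elsewhere in Section 7.9.1.

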### **7.9.2 Analysis of Key Secondary Efficacy Endpoint**

The primary analysis of change from Baseline in CSFT at Week 12 will be performed using an ANCOVA model including fixed effect for treatment and Baseline CSFT score as a covariate. Missing data or data after receipt of rescue medication will be imputed using WOCF. Selected sensitivity analyses like those identified for the primary efficacy endpoint may also be performed. Analysis will be performed separately to compare each dose of MT-0814 to placebo (eg, including only subjects receiving placebo and subjects receiving the MT-0814 dose being compared to placebo).

### **7.9.3 Analyses of Other Secondary Efficacy Endpoints**

Endpoints for changes from Baseline at each visit will be analyzed using an ANCOVA model, applying treatment as fixed effect and the parameter's Baseline value as the covariate, utilizing WOCF for missing data or treatment data occurring after receipt of rescue therapy. The t-tests will also be performed for changes from Baseline. Endpoints for proportions of subjects will be analyzed using Fisher's Exact test. Kaplan-Meier estimates will be presented for the time to receipt of rescue therapy.

Analyses will be performed separately to compare each dose of MT-0814 to placebo (eg, including only subjects receiving placebo and subjects receiving the MT-0814 dose being compared to placebo).

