- Total lesion area (as measured by fluorescein angiography [FA], indocyanine green angiography [ICGA], and color fundus photography [CFP])
- Choroidal neovascularization area (as measured by FA, ICGA, and CFP)
- Leakage area (as measured by FA, ICGA, and CFP)
- Regression of polypoidal choroidal vasculopathy (PCV)
- Proportions of subjects requiring anti-VEGF rescue therapy
- Proportions of subjects who achieve dry retina (defined as an absence of visible intraretinal cystoid edema or subretinal fluid on OCT scan) at Weeks 4, 8, 12 (EOT), and 16 (EOS).
- Duration from start of treatment (SOT) to the time that anti-VEGF rescue therapy is initiated.
- Other safety measures include monitoring of AEs, ophthalmological assessments (visual acuity, FA/ICGA, CFP, slit-lamp biomicroscopy examinations, and measurement of intraocular pressure [IOP]), physical examination findings, vital sign measurements, ECG findings, clinical laboratory tests, and monitoring of concomitant medications.
- Predose and 2-hour postdose plasma concentrations of MT-0814 and its metabolites M5 and M6 on Days 1, 29, 57, and 85 of the study.

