### **4.2.2 Handling of Withdrawals**

Subjects who discontinue study treatment or active participation in the study will no longer receive study drug. When a subject withdraws from the study, the reason(s) for withdrawal shall be recorded by the investigator on the relevant page of the eCRF. Whenever possible, all subjects who permanently discontinue study treatment or withdraw from the study

prematurely will undergo all EOS assessments (for subjects who withdraw before Week 16). Subjects who fail to return for final assessments will be contacted by the site in an attempt to have them comply with the protocol. If the subject is unreachable by telephone, a registered letter, at the minimum, should be sent to the subject requesting that he or she should contact the study site.

All subjects who withdraw from the study with an ongoing AE must be followed until the AE is resolved or deemed stable.

All subjects who withdraw from the study due to pregnancy must be followed to record the outcome of the pregnancy. See Section 6.3 for further information on the procedures for following female subjects who become pregnant during the study.

If a subject withdraws prematurely after dosing, all data to be collected prior to discharge from the study site should be collected at the time of premature discontinuation or at the scheduled EOS visit.

It is vital to obtain follow-up data on any subject withdrawn because of an AE or SAE. In every case, efforts must be made to undertake protocol-specified, safety, follow-up procedures. If study drug is interrupted for a safety reason, it is at the discretion of the investigator whether to continue treatment with the study drug.

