## 6 Study Assessments and Procedures

Before performing any study procedures, all potential subjects will sign an ICF. Potential subjects will have the opportunity to have any questions answered before signing the ICF. The investigator must address all questions raised by the potential subject. The investigator (or designee) will also sign the ICF.

The EOT visit is defined as the visit occurring at the end of the 12-week treatment period (Week 12) or the final visit at which the subject is permanently discontinued/withdrawn from study drug administration. The EOS visit is defined as the visit occurring at the end of the 16-week study period (Week 16) or the final visit at which the subject is permanently discontinued/withdrawn from participation in the study.

The SOE is presented in Section 13 (Table 13–1). On Day 1 (SOT) and the EOT visit, all scheduled assessments must be completed in a single day. For all other visits, in the event that all of the scheduled assessments cannot be completed in a single day, the site staff must ensure that BCVA-ETDRS and OCT scan are performed on the same day.

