#### 6.1.2 Optical Coherence Tomography

Optical coherence tomography will be performed with pupil dilation at every study visit as indicated in the SOE (Table 13–1). Optical coherence tomography will be performed on both the study and fellow eye of each subject at Screening, Day 1, the EOT visit, and the EOS visit. At all other visits, OCT scan will be performed on the study eye only.

Central subfield thickness will be measured at every visit via OCT scan. Assessment of dry retina (defined as an absence of visible intraretinal cystoid edema or subretinal fluid on OCT scan) will be performed on Day 1, Week 4, Week 8, the EOT visit, and the EOS visit. Refer to the *MT-0814 Ophthalmology Procedure Manual* for detailed instructions on the OCT procedure, as well as the assessments of CSFT and dry retina.

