- a) At this visit, subjects who meet all eligibility criteria for the study will be randomly assigned in a 3:3:1 ratio to receive MT-0814 [REDACTED] MT-0814 [REDACTED] or placebo [REDACTED]. All randomized subjects will be administered their first dose of study drug during this visit (preferably before 12 PM [Noon]).
- b) The assessments included in this column must be conducted at the last subject visit for those who are discontinued or withdraw from the study before receiving 12 weeks of treatment.
- c) The assessments included in this column must be conducted at the last subject visit for those who are discontinued or withdraw from the study before the end of the 4-week follow-up period.
- d) Both the study eye **and** fellow eye will be assessed at Screening, Day 1 (no color fundus photography, FA, or ICGA assessments on Day 1), Visit 14 (Week 12; EOT), and the EOS/discontinuation visit (Visit 18 [Week 16] or early discontinuation/withdrawal). At all other indicated visits, only the study eye will be assessed.
- e) Assessment of dry retina (defined as an absence of visible intraretinal cystoid edema or subretinal fluid on OCT scan) will be performed at Visit 2 (Day 1), Visit 6 (Week 4), Visit 10 (Week 8), Visit 14 (Week 12; EOT), and the EOS/discontinuation visit (Visit 18 [Week 16] or early discontinuation/withdrawal).
- f) The FA will be performed at all sites; select sites will also perform ICGA in addition to FA.
- g) Blood pressure, pulse, body temperature, and body weight will be assessed at all indicated visits; height will only be assessed at Visit 1.

Visit No.	1	2 a (RAN/ SOT)	3	4	5	6	7	8	9	10	11	12	13	14 b (EOT)	15	16	17	18 c (EOS)
Study Week	-2	0	1	2	3	4	5	6	7	8	9	10	11	12	13	14	15	16
Study Day: (Allowance):	≤14 Days Before Day 1	1	8 (±2)	15 (±2)	22 (±2)	29 (±2)	36 (±2)	43 (±2)	50 (±2)	57 (±2)	64 (±2)	71 (±2)	78 (±2)	85 (±2)	92 (±2)	99 (±2)	106 (±2)	113 (±2)

h) The detailed blood sample collection schedule for plasma concentration analyses is presented in Table 13–2.

i) Female subjects only. Day 1 urine dipstick pregnancy test will only be administered to female subjects who are either premenopausal or have been postmenopausal for <1 year.

**Note:** If a female subject has a positive pregnancy test result (serum and/or urine dipstick) but the investigator suspects that the result is a false positive, the female subject can participate in the study at the investigator's discretion.

[REDACTED]

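### Does Section 7.9.3 need a rule for rescued subjects in the dry-retina proportions?

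*Combined protocol and SAP*

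**What the plan says.** Section 7.3 lists the proportion of subjects with a dry retina at Weeks 4, 8, 12 and 16 among the other secondary endpoints. Section 7.9.3 gives the analysis: "Endpoints for proportions of subjects will be analyzed using" Fisher's exact test, each dose against placebo. For changes from Baseline at each visit, the same section specifies ANCOVA, "utilizing WOCF for missing data or treatment data occurring after receipt of rescue therapy". That clause belongs to the ANCOVA sentence and is not repeated for proportions.

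Both results come from optical coherence tomography (OCT). Section 6.1.2 says "Central subfield thickness will be measured at every visit via OCT scan", and that the dry-retina assessment "will be performed on Day 1, Week 4, Week 8, the EOT visit, and the EOS visit".

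Several sections bear on the timing of the last reading:

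- Section 3.1 lists the dry-retina proportions "at Weeks 4, 8, 12 (EOT), and 16 (EOS", tying Week 12 to the end-of-treatment (EOT) visit and Week 16 to the end-of-study (EOS) visit.
- Section 6 places the EOS visit at the end of the study period ("Week 16) or the final visit at which the subject is permanently discontinued/withdrawn from participation in the study").
- Table 13–1, footnote e, includes among the reading times "Visit 10 (Week 8), Visit 14 (Week 12; EOT), and the EOS/discontinuation visit (Visit 18 [Week 16] or early discontinuation/withdrawal".
- Section 4.2.2 asks for EOS assessments, where possible, from subjects who stop treatment. For a subject who withdraws early, it says data "should be collected at the time of premature discontinuation or at the scheduled EOS visit".
- Section 4.2.3 calls a rescued subject a treatment failure, stops study drug, starts anti-VEGF injections and has the EOT evaluations done when failure is declared. It does not say whether the subject leaves the study.

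Section 7.9 places data conventions in the SAP. Section 8 has the SAP approved and signed before the database is locked.

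**The concern.** Two results from one type of scan appear to be handled differently. A CSFT value recorded after rescue is replaced by the worst earlier value, but nothing is said about a dry-retina status recorded after rescue. If that status were counted as observed, an eye dried by anti-VEGF would be a responder in its randomised arm, although Section 4.2.3 calls the subject a treatment failure.

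The EOS label adds a second doubt. A rescued subject's last reading might be taken near the rescue decision, or at Week 16 after several weeks of anti-VEGF. The two could give opposite answers.

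With five placebo subjects, one or two such eyes would visibly change the dry-retina comparison, in either direction if rescue differs between arms.

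**Working it through.** **Inputs.** About 35 subjects at 3:3:1 (Sections 3.1 and 7.4); two-sided 5% tests without multiplicity adjustment (Section 7.9); nominal study days (Table 13–1). The documents give no rescue rate and no expected dry-retina rate, so all counts in steps 3 and 4 are assumptions.

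**1. Group sizes.** 35 × 3/7 = 15 per dose and 35 × 1/7 = 5 on placebo, as Section 3.1 states.

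**2. One subject.** 1/5 = 20.0 points on placebo; 1/15 = 6.7 points in a dose arm.

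**3. Effect on the difference.** Let d_a and d_p be the rescued eyes read as dry in the dose arm and on placebo. Counting them as observed instead of as not dry changes the difference (dose minus placebo) by d_a/15 − d_p/5:

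| d_p | d_a | Change (points) |
|---|---|---|
| 1 | 3 | 20.0 − 20.0 = 0 |
| 1 | 2 | 13.3 − 20.0 = −6.7 |
| 2 | 3 | 20.0 − 40.0 = −20.0 |
| 1 | 6 | 40.0 − 20.0 = +20.0 |

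The change is zero whenever the rescued-and-dry percentages match between arms.

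**4. Two worked cases.** All rescued eyes are assumed dry later, no unrescued placebo eye is dry, and 9 of 12 unrescued dose-arm eyes are dry. P-values are two-sided Fisher.

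| Handling of rescued subjects | Unequal rescue (2/5 v 3/15) | Equal rescue (1/5 v 3/15) |
|---|---|---|
| Not dry | 9/15 v 0/5: 60 points, p=0.038 | 9/15 v 0/5: 60 points, p=0.038 |
| As observed | 12/15 v 2/5: 40 points, p=0.131 | 12/15 v 1/5: 60 points, p=0.031 |
| Excluded | 9/12 v 0/3: 75 points, p=0.044 | 9/12 v 0/4: 75 points, p=0.019 |

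The excluded p-values are C(6,3)/C(15,3) = 20/455 = 0.044 and C(7,4)/C(16,4) = 35/1820 = 0.019. The convention can matter in so small a study, but under equal rescue counting as observed leaves the difference where it was.

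**5. Timing.** From the visit at which failure is declared to Week 16 (Day 113): Week 1, 113 − 8 = 105 days; Week 8, 113 − 57 = 56; Week 11, 113 − 78 = 35. A late reading on a rescued subject would thus be well separated from one at the rescue decision.

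**6. What the sections imply together.**

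- Section 7.9.3 names a test for proportions. It does not say which readings make a subject dry, so it does not say that a post-rescue dry eye is a responder.
- Section 4.2.3 gives the rescued subject a status, treatment failure. Sections 7.9.1 to 7.9.3 discard post-rescue values for every change endpoint. Both point to counting the subject as not dry.
- A WOCF-style rule for a yes/no result would nearly always agree. Inclusion criterion 7 requires retinal or subretinal fluid at Screening, and the worst earlier reading is not dry unless every postbaseline reading before rescue was dry.
- Once a rescued subject counts as not dry, it no longer matters which of the two possible EOS readings exists, because neither is used after rescue.
- For a subject who leaves early without rescue, Section 7.3 defines the endpoint by week. Section 6 and footnote e say when procedures are done; they do not say that an early EOS reading is analysed as Week 16.

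**The case for a change.** The best case for a change is that the convention is cheap to state and is stated nowhere in the supplied text. In the unequal-rescue case the same data give p=0.038 or p=0.131 depending on the convention, so a rule chosen after unmasking would be open to criticism. The parenthesis in Section 3.1 and footnote e lend some support to treating an early EOS reading as Week 16.

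Part of this stands. The handling of rescued and missing subjects in the proportions, and the denominator, are not in the supplied text. Sections 3.1, 4.2.2, 4.2.3, 5.8.2 and 6 also do not settle whether a rescued subject stays to Week 16; Section 5.8.2 lists intravitreal anti-VEGF to the study eye as prohibited through EOS, while Section 4.2.2 still seeks EOS assessments after treatment stops.

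The rest does not carry. Deriving a yes/no status and assigning visits to weeks are data conventions, which Section 7.9 sends to the SAP; their absence here is not evidence that they are absent there. That SAP is signed before lock, which guards against a results-driven choice. The p-values on either side of 5% come from invented counts, with every rescued eye dry and no unrescued placebo eye dry. Nor is Week 16 special: the same silence covers Weeks 4, 8 and 12. The letter-change categories can be taken directly from the WOCF-imputed Week 12 acuity of Section 7.9.1.

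**Conclusion.** No change to the plan follows. This is a gap that analysts fill sensibly: the treatment-failure status and the rescue rules for the other endpoints lead to counting rescued subjects as not dry, and the week-based definition leads to placing readings by actual date. How subjects missing without rescue enter the denominator is an ordinary SAP convention.

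The possible effect is 20 points per placebo subject and 6.7 per dose-arm subject, and nil on the difference when rescued-and-dry percentages are equal. It concerns secondary proportions tested without multiplicity adjustment, in a proof-of-concept study whose size was not set by power (Section 7.4). The primary acuity analysis (Section 7.9.1) and the key secondary CSFT analysis (Section 7.9.2) state their rescue handling and are unaffected. Rescue rate and time to rescue are reported as endpoints in their own right, so a reader can see whether rescue differed between arms.

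The conclusion assumes that the SAP records the convention before lock, as Sections 7.9 and 8 provide, and that it follows Section 4.2.3. The supplied text neither confirms nor contradicts this.
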